1.2. Study Design

Study ALXN1210-NEPH-202 is a Phase 2, randomized, double-blind, placebo-controlled, multicenter study of ravulizumab in addition to allowed concomitant therapy consistent with the standard of care in 120 adult participants (18 to 75 years of age) with either proliferative LN or IgAN. All participants must be naïve to complement inhibitor treatment and have either a diagnosis of LN with an active flare or IgAN based on kidney biopsy, eGFR \geq 30 mL/min/1.73 m², and proteinuria (defined as UPCR \geq 1 g/g from one 24-hour urine collection [LN cohort] or as mean protein \geq 1 g/24-h from 2 valid 24-hour collections [IgAN cohort]). Participants in the IgAN cohort must have been treated with stable doses of the maximum tolerated renin-angiotensin system (RAS)-inhibiting medications and have controlled, stable blood pressure (< 140/90 mmHg) for \geq 3 months prior to Screening.

Approximately 60 participants in each disease cohort will be randomly assigned in a 2:1 ratio to receive ravulizumab or placebo (40 ravulizumab, 20 placebo). Randomization will be stratified by whether corticosteroid induction treatment was initiated prior to Screening versus during the Screening Period for participants in the LN cohort and by mean proteinuria (1 to 2 g/day versus > 2 g/day) from 2 valid 24-hour urine collections during the Screening Period for participants in the IgAN cohort.

The study consists of an up to 6-week Screening Period, a 26-week Initial Evaluation Period, a 24-week Extension Period, and a 36-week Post-treatment Follow-up Period. Thus, the total treatment duration is 50 weeks and the total study duration is up to 86 weeks ([Figure 1](#) and [Figure 2](#)).

During the Initial Evaluation Period, all participants will receive a weight-based loading dose of ravulizumab or placebo on Day 1, followed by maintenance doses of ravulizumab or placebo on Day 15 and then q8w thereafter. Loading and maintenance doses will be determined based on body weight. All participants will receive allowed concomitant therapy consistent with the standard of care for participants with LN and IgAN throughout the study.

[figure not shown]
During the 24-week Extension Period, participants in the LN cohort will continue to receive their randomized allocation of study intervention (ravulizumab or placebo) q8w. For the IgAN cohort, participants in the placebo treatment group will receive a blinded loading dose of ravulizumab at Week 26, and participants in the ravulizumab treatment group will receive a blinded ravulizumab dose of 900 mg at Week 26. Starting at Week 28, all participants in the IgAN cohort will receive open-label weight-based doses of ravulizumab q8w until the end of the Extension Period.

During the 36-week Post-treatment Follow-up Period, all participants will continue to receive standard of care and will be monitored for safety, clinical events of interest, and kidney function. Participants who discontinue study intervention early and agree to remain in the study should continue to attend their scheduled protocol visits until Week 50. During these visits, all assessments except for administration of study intervention should be performed according to the Schedule of Assessments. Participants who withdraw from the study will be followed for safety until 8 weeks after the last dose of study intervention. The end of study is defined as the last participant's last visit in the Post-treatment Follow-up Period.

In the LN cohort, participants will receive additional standard-of-care therapy in the event of a protocol-defined renal flare or severe extrarenal SLE flare. After Week 26, participants may also receive additional standard-of-care therapy for protocol-defined suboptimal response.

The primary objective of the study is to evaluate the efficacy of ravulizumab compared with placebo to reduce proteinuria in adult participants with LN or IgAN.

Figure 1: Study Design Schematic – LN Cohort

[figure not shown]

Note: Randomization will be stratified by whether corticosteroid induction treatment was initiated prior to Screening versus during the Screening Period. Allowed concomitant therapy consists of corticosteroids and mycophenolate mofetil. Weight-based dosing regimen (see [Protocol Section 1.1](#)) will be based on the last recorded study visit body weight.

^a Participants will receive additional standard-of-care therapy in the event of a protocol-defined renal flare or severe extrarenal SLE flare. Approved novel treatment(s) for LN is allowed. After Week 26, additional standard-of-care therapy for participants with suboptimal response is allowed at the clinical discretion of the Investigator in conversation with the Medical Monitor.

Abbreviations: LN = lupus nephritis; PK = pharmacokinetics

Figure 2: Study Design Schematic – IgAN Cohort

Note: Randomization will be stratified by mean proteinuria (1 to 2 g/day versus > 2 g/day) based on 2 valid 24-hour urine collections during the Screening Period. Allowed concomitant therapy consisting of stable maximally tolerated dose of ACE inhibitors or ARBs. Weight-based dosing regimen (see [Protocol Section 1.1](#)) will be based on the last recorded study visit body weight.

Abbreviations: ACE = angiotensin-converting enzyme; ARB = angiotensin II receptor blocker;
IgAN = immunoglobulin A nephropathy; PK = pharmacokinetics

2. STATISTICAL HYPOTHESES

The primary hypothesis for this study is that ravulizumab is superior to placebo in decreasing proteinuria. Hypothesis testing will be one-sided and performed at the 0.05 level of significance.

3. SAMPLE SIZE DETERMINATION

This study plans to enroll 60 participants in both the IgAN and LN cohorts in a 2:1 ratio to ravulizumab and placebo for a total of 120 participants.

In March 2018, a National Kidney Foundation-sponsored workshop on surrogate endpoints for clinical studies in early stages of chronic kidney disease proposed that a 20% to 30% reduction in the geometric mean of albuminuria or proteinuria was likely to be necessary to ensure a significant treatment effect on the clinical outcome ([Levey, 2020](#)).

Individual patient data from relevant studies in IgAN was previously used to estimate variability and expected changes in proteinuria for patients treated with placebo in addition to background standard-of-care treatment ([Fellstrom, 2017](#)). Based on these data, the geometric mean (GM) of the ratio of 26-week to baseline proteinuria values is assumed to be 0.85 (ie, a 15% reduction in proteinuria) for the placebo treatment group. In order to target at least a 30% relative treatment effect (ie, 1 minus geometric mean ratio [GMR] of ravulizumab to placebo at Week 26), the GM of the ratio of 26-week to baseline is assumed to be 0.55 (ie, a 45% reduction in proteinuria) for the ravulizumab treatment group.

Expected changes in proteinuria and associated variability were not available on the log-scale for patients with LN; however, 2 studies of patients with LN who were treated with mycophenolate mofetil (MMF) showed mean proteinuria values of approximately 4.0 g/day at baseline and approximately 2.0 g/day at Week 24 ([Appel, 2009](#); [Ginzler, 2005](#)). The GM of the ratio of 26-week to baseline proteinuria values is assumed to be 0.60 (ie, a 40% reduction in proteinuria) for the placebo treatment group. In order to target at least a 30% relative treatment effect, the GM of the ratio of 26-week to baseline proteinuria values is assumed to be 0.40 (ie, a 60% reduction in proteinuria) for the ravulizumab treatment group.

Sample size calculations are based on a 1-sided, 2-sample t-test of log-transformed proteinuria values. The log change from baseline in proteinuria is calculated as $\log(0.85)$ and $\log(0.55)$ for the placebo and ravulizumab treatment groups, respectively, for the IgAN cohort and as $\log(0.60)$ and $\log(0.40)$ for the placebo and ravulizumab treatment groups, respectively, for the LN cohort. A common standard deviation (SD) of log change is assumed to be 0.60 ([Fellstrom, 2017](#)). Under these assumptions and an anticipated 10% drop out rate, a sample size of 60 participants (40 participants randomized to ravulizumab, 20 participants randomized to placebo) will provide approximately 80% power to detect a treatment difference with a 1-sided significance level of 0.05 in each cohort.

4. ANALYSIS SETS

The following populations are defined for this study:

Analysis Set	Description
Randomized Set	All randomized participants. Participants will be analyzed as randomized for reporting disposition.
Full Analysis Set (FAS)	All randomized participants who receive at least 1 dose of the study intervention. Participants will be analyzed as randomized for reporting efficacy data.
Modified Full Analysis Set (mFAS)	
All FAS participants excluding participants who were impacted by COVID-19 as follows:
 
 1. Participants who received a dose of ravulizumab \geq 28 days after the scheduled dosing time point or missed a dose altogether during the 26-week Initial Evaluation Period due to COVID-19 2. Participants who withdrew from the study early during the 26-week Initial Evaluation Period due to COVID-19 3. Participants who received concomitant treatments for COVID-19 during the 26-week Initial Evaluation Period that could potentially affect efficacy 4. Participants who were hospitalized due to a COVID-19-related AE during the 26-week Initial Evaluation Period 
Inclusion in the mFAS will be determined for each participant prior to database lock.

Per-Protocol Set (PPS)	
All randomized participants who receive at least 1 dose of study intervention and without important protocol deviations who meet the following criteria:
 
 1. For LN cohort, satisfied the following inclusion criteria (IC)/exclusion criteria (EC): 
 – IC #10: Diagnosis of LN Class III or IV confirmed by biopsy – IC #12: Proteinuria with UPCR \geq 1 g/g based on one 24-hour urine collection during the Screening Period – EC #1: eGFR $<$ 30 mL/min/1.73 m² during Screening – EC #20: Received any of the specified treatments (see Protocol Section 5.2.2) 2. For IgAN cohort, satisfied the following inclusion/exclusion criteria: 
 – IC #13: Established diagnosis of primary IgAN based on kidney biopsy – IC #14: Mean proteinuria \geq 1 g/day on 2 complete and valid 24-hour urine collections during the Screening Period

Analysis Set	Description
	
 – IC #16: Compliance with stable and optimal dose of RAS inhibitor treatment for \geq 3 months prior to Screening – EC #1: eGFR $<$ 30 mL/min/1.73 m² during Screening 
3. For LN cohort, received appropriate additional standard-of-care therapy, if required per protocol, during the 26-week Initial Evaluation Period
 
4. Received appropriate allowed concomitant therapy during the 26-week Initial Evaluation Period
 
5. Received all planned number of doses during the 26-week Initial Evaluation Period
 
6. Received correct treatment per randomization schedule
 
7. Did not receive any disallowed medications or therapies during the 26-week Initial Evaluation Period (see Protocol Section 6.7.2)
 
8. Was not unblinded to treatment allocation during the 26-week Initial Evaluation Period
 
Inclusion in the PPS will be determined for each participant prior to database lock.

Safety Set	All participants who receive at least 1 dose of study intervention. Participants will be analyzed according to the study intervention they actually received for reporting exposure and safety data.
PK Analysis Set	All participants who receive at least 1 dose of study intervention and who have evaluable PK data.
PD Analysis Set	All participants who receive at least 1 dose of study intervention and who have evaluable PD data.

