9.3. Populations for Analyses

The following populations are defined for this study:

Population	Description
Randomized Set	All randomized participants. Participants will be analyzed as randomized for reporting disposition, demographics, and baseline characteristics.
Full Analysis Set (FAS)	All randomized participants who receive at least 1 dose of study drug. Participants will be analyzed as randomized for reporting efficacy data.
Modified Full Analysis Set (mFAS)	The mFAS is a subset of the FAS, excluding participants who were impacted by COVID-19.
Safety Set	All participants who receive at least 1 dose of study drug. Participants will be analyzed according to the study drug they actually received for reporting exposure and safety data.
Per Protocol Set	All randomized participants who receive at least 1 dose of study drug and without important protocol deviations.
Pharmacokinetic (PK) Analysis Set	All participants who receive at least 1 dose of study drug and who have evaluable PK data.
Pharmacodynamic (PD) Analysis Set	All participants who receive at least 1 dose of study drug and who have evaluable PD data.

Abbreviations: PD = pharmacodynamic; PK = pharmacokinetics

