5.3.4. Supplementary Analysis

[Table 3](#) shows the supplementary analyses that will be produced for the primary endpoint.

Table 3: Supplementary Analyses

Supplemental Analysis	Methodology	Population	Handling of Intercurrent Events
Randomized Set analysis	ANCOVA	Randomized Set	
 - Data collected on or after receipt of additional standard-of-care therapy (for the LN cohort only) will be imputed using the value collected at the time of renal flare or extrarenal SLE flare - Data collected on or after treatment discontinuation will be imputed using multiple imputation
mFAS analysis	ANCOVA	mFAS	
 - Data collected on or after receipt additional standard-of-care therapy (for the LN cohort only) will be imputed using the value collected at the time of renal flare or extrarenal SLE flare - Data collected on or after treatment discontinuation will be imputed using multiple imputation
PPS analysis	ANCOVA	PPS	
 - Data collected on or after receipt of additional standard-of-care therapy (for the LN cohort only) will be imputed using the value collected at the time of renal flare or extrarenal SLE flare - Data collected on or after treatment discontinuation will be imputed using multiple imputation
Treatment policy analysis	ANCOVA	FAS	
 - All observed data is used regardless of receipt of additional standard-of-care therapy (for the LN cohort only) or treatment discontinuation.

Abbreviations: ANCOVA = analysis of covariance; mFAS = Modified Full Analysis Set; FAS = Full Analysis Set; LN = lupus nephritis; PPS = Per-protocol Set; SLE = systemic lupus erythematosus

Further details of these supplementary analyses are below.

- Randomized Set analysis: The primary endpoint will be analyzed in the same manner as the primary analysis, except using the Randomized Set instead of the FAS. The Randomized Set will only be analyzed if the FAS population excludes more than 10% of the Randomized Set.
- mFAS analysis: The primary endpoint will be analyzed in the same manner as the primary analysis, except using the mFAS instead of the FAS. The mFAS will only be analyzed if this population excludes more than 10% of the FAS.
- PPS analysis: The primary endpoint will be analyzed in the same manner as the primary analysis, except using the PPS instead of the FAS.

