6.2.4. Protocol Deviations

Protocol deviations will be determined per the standard operating procedure “Identification, Handling, and Documentation of Protocol Deviations” (SOP-G-CL-0044). The number and percent of patients with specific protocol deviations will be summarized for all enrolled participants by important and nonimportant deviations. Protocol deviations will be presented overall as well as separately for those related to COVID-19.

To ensure completeness of the list of protocol deviations, the following will be verified programmatically from the database:

1. Participants from whom informed consent was not obtained
2. Participants who violated any inclusion/exclusion criteria.
3. Participants who received any disallowed medication or therapy
4. Participants randomized to the ravulizumab treatment group who did not receive all of the planned number of doses during the 26-week randomized treatment period.

Protocol deviations from monitoring reports and other relevant sources will also be reviewed, and any important deviations will be included in the list that is summarized and reported.

Summary statistics will be presented by treatment group and overall.

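### The late-dose exclusion in the SAP's mFAS names ravulizumab only, so a placebo participant with the same COVID-19 dosing delay stays in that supplementary analysis set

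*SAP*

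**What the plan says.** Protocol Section 9.3 is arm-neutral: "The mFAS is a subset of the FAS, excluding participants who were impacted by COVID-19".

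SAP Section 4 turns this into four criteria. The first covers "Participants who received a dose of ravulizumab" at least "28 days after the scheduled dosing time point or missed a dose altogether during the 26-week Initial Evaluation Period due to COVID-19". The other three (early withdrawal, concomitant COVID-19 treatment that could affect efficacy, COVID-19 hospitalization) name no arm; the second, for example, reads "Participants who withdrew from the study early during the 26-week Initial Evaluation Period due to COVID-19". On timing, the SAP says: "Inclusion in the mFAS will be determined for each participant prior to database lock".

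SAP Section 5.3.4 makes the analysis conditional: "The mFAS will only be analyzed if this population excludes more than 10% of the FAS". The primary analysis uses the FAS (SAP Section 5.3).

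On deviations, SAP Section 6.2.4 lists four items to be verified by program. Item 4 is "Participants randomized to the ravulizumab treatment group who did not receive all of the planned number of doses during the 26-week randomized treatment period". The same section also has deviations from monitoring reports and other sources reviewed. The per-protocol set carries its own dosing condition, with no arm named: "Received all planned number of doses during the 26-week Initial Evaluation Period".

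**The concern.** An exclusion based on a post-randomisation event should apply by the same rule in both arms. Here the late-dose limb depends on which product was infused. Two participants with the same delay for the same reason are treated differently: the one on ravulizumab leaves the mFAS and the one on placebo stays. Membership under this limb therefore depends on the treatment code.

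Two things are at stake, both within the mFAS analysis. The count toward the 10% trigger leaves out late-dosed placebo participants, so the analysis may not be run when COVID-19 disruption was common enough to call for it. If it is run, the arms are selected differently.

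A related but separate point is that the programmed completeness check for missed doses looks at one arm only, which may leave the deviation summary less complete for placebo.

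**Working it through.** **Reading the rules side by side**

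- Late dose (mFAS criterion 1, first limb): ravulizumab named.
- Missed dose (criterion 1, second limb): no product named; the natural reading covers both arms.
- mFAS criteria 2 to 4: both arms.
- PPS criterion 5: both arms, missed doses only.
- Programmed missed-dose check (SAP 6.2.4 item 4): ravulizumab arm only.
- Protocol 9.3 definition of the mFAS: both arms.
- SAP Appendix 5 (changes to protocol-planned analyses): only the hematuria change is listed.

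The Week 26 dose does not rescue the wording for IgAN placebo participants. They first receive ravulizumab then, but SAP Section 5.1.1 makes that dose the start of the Extension Period, outside the window of criterion 1.

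**Effect on the trigger**

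Inputs: 40 ravulizumab and 20 placebo participants per cohort (SAP Section 3), taking all 60 as dosed and so in the FAS. The documents give no late-dose rate, so a common share *f* in each arm is assumed, with no exclusions under any other limb. More than 10% of 60 means at least 7 exclusions. As written, all 7 must come from ravulizumab (7/40 = 17.5% of that arm); under an arm-neutral rule any 7 of 60 suffice (11.7%).

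| *f* (assumed) | Removed as written, *f* × 40/60 | Removed arm-neutral, *f* | Run as written? | Run arm-neutral? |
|---|---|---|---|---|
| 10% | 4/60 = 6.7% | 6/60 = 10.0% | no | no |
| 12% | 4.8/60 = 8.0% | 7.2/60 = 12.0% | no | yes |
| 15% | 6/60 = 10.0% | 9/60 = 15.0% | no | yes |
| 20% | 8/60 = 13.3% | 12/60 = 20.0% | yes | yes |

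The 12% row uses expected counts. A whole-number case close to it is 5 of 40 and 2 of 20 late: 5/60 = 8.3% as written against 7/60 = 11.7% arm-neutral. On these assumptions the two rules disagree about running the analysis when *f* is above 10% and up to 15%.

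**Effect on the estimate, if the analysis is run**

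Both rules remove the same late-dosed ravulizumab participants, so the ravulizumab mean is the same under either. The difference lies in the placebo arm. Let late-dosed placebo participants have a log change in proteinuria worse by *h* than other placebo participants. Keeping them raises the placebo mean by *f* × *h*, so

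GMR as written = GMR arm-neutral × exp(−*f* × *h*).

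The planning values give arm-neutral GMRs of 0.55/0.85 = 0.647 (IgAN) and 0.40/0.60 = 0.667 (LN). The value of *h* is also an assumption; 0 to 0.2 is shown.

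| *f* | *h* | IgAN GMR as written | LN GMR as written |
|---|---|---|---|
| any | 0 | 0.647 | 0.667 |
| 10% | 0.2 | 0.634 | 0.653 |
| 12% | 0.2 | 0.632 | 0.651 |
| 20% | 0.2 | 0.622 | 0.641 |

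The largest shift is 0.20 × 0.2 = 0.04 log units, against assumed effects of ln(0.85/0.55) = 0.435 and ln(0.60/0.40) = 0.405. That is about 9% and 10% of the effect. With late doses as the only exclusions, just the 20% row passes the trigger as written; the 10% and 12% rows would matter only if other criteria took the total above 10%.

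**The case against.** The strongest reply is that this is a drafting slip in an optional analysis. The primary comparison is on the FAS, the Protocol definition is neutral, and Randomized Set (itself conditional), per-protocol and treatment-policy analyses sit alongside the mFAS. That stands, and it limits the importance of the point. It does not make the written rule right.

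Several stronger readings are tempting, and the documents do not support them.

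- *Placebo participants who missed a dose also stay in.* That phrase names no product and naturally covers both arms. It could be read as referring back to ravulizumab, which is a reason to reword but not a finding.
- *The SAP contradicts itself, because PPS criterion 5 is neutral.* That criterion concerns missed doses, not late ones, and defines a different set.
- *The deviation table will show an excess on ravulizumab.* Monitoring reports are reviewed without restriction by arm. SAP 5.6.1 summarises missed infusions and their reasons by treatment group, and SAP 5.7.3 lists COVID-19 disruptions for all participants. Ascertainment may be unequal; an excess is not established. Nor does item 4 define the mFAS.
- *The rule cannot be applied blind.* Late infusions could be flagged blind in both arms and the code applied afterwards, and PPS criterion 6 also needs the code. What stands is that late-dose membership depends on treatment assignment.
- *Removing late-dosed ravulizumab participants is itself the bias.* The corrected rule removes the same people. If delay matters only through lost drug exposure, a late placebo infusion changes nothing, and the two rules give the same expected effect.

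**Conclusion.** The point holds for the late-dose limb of mFAS criterion 1. Read literally, it excludes late-dosed participants from one randomised arm only, departs from the Protocol's definition, and is not declared in SAP Appendix 5.

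The consequence is limited to the conditional mFAS analysis. Assuming equal late-dosing in both arms and no other exclusions, the written rule counts two-thirds of the late-dosed participants toward the trigger (8% instead of 12% of the FAS at a 12% rate). If the analysis runs, the contrast moves toward ravulizumab by *f* × *h*: zero if late-dosed placebo participants fare like other placebo participants, and up to 0.04 log units over the assumed range. The late-dosing rates and the outcome difference are illustrations, not figures from the documents. With late doses as the only exclusions, the two harms are alternatives: where the trigger is missed there is no mFAS estimate to bias.

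A reader might infer that the trial's randomised comparison is compromised. It is not, because the primary FAS analysis does not use this rule. The one-arm check in SAP 6.2.4 item 4 is a smaller, separate matter of possibly unequal deviation ascertainment.

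**What to change.** - In mFAS criterion 1, replace the reference to a dose of ravulizumab with *a dose of study intervention (ravulizumab or placebo)*, so that the late-dose and missed-dose limbs both clearly apply to both arms.
- In SAP 6.2.4 item 4, replace the reference to participants randomized to ravulizumab with *Participants*.
- State that late- and missed-dose status is determined from infusion records without reference to treatment assignment.

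The cost is two wording changes and one added sentence in the SAP. No new data are needed, and the mFAS returns to the Protocol's definition.
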